2.4.2 Rationale for dose selection (entospletinib)

The initial dose level tested is proposed to be 200 mg of entospletinib administered twice daily combined with the FDA-approved dosing of obinutuzumab.

Entospletinib has been well tolerated at doses of up to 800 mg twice daily in patients with CLL using first formulation (Mono-MSA ENTO) [29]. The dose and schedule used in the monotherapy setting resulted in consistent inhibition of a biomarker of SYK activity over the dosing interval. The dose of 400 mg twice daily using a second formulation (Bis-MSA SD ENTO) yields a PK distribution biologically equivalent to 800 mg twice daily the first entospletinib formulation (see Investigator's Brochure for details). A 200 mg once daily dose of entospletinib is expected to provide plasma concentrations above EC50 for approximately 12 hours a day and it is anticipated that target inhibition by entospletinib will be approximately 24% at trough drug levels. A starting dose of 200 mg of entospletinib twice daily is 1/4th of the total daily dose that has been shown to be well-tolerated in patients. If tolerated, the dose of entospletinib will subsequently be escalated to 400 mg twice daily.

2.5 Correlative studies background

2.5.1. Assessment of B-cell depletion

Entospletinib and obinutuzumab target B-cell survival via distinct mechanisms, as discussed above. Therefore, CD19 $^{+}$ B-cell counts will be assessed over time in this study.

2.5.2. Pharmacodynamic endpoints

Lymph nodes and bone marrow are the sites of CLL cell proliferation, with expression of gene signatures indicating activation of the BCR and nuclear factor- κ B (NF κ B) pathways [32, 33]. Interactions between the malignant B cells and mesenchymal stromal cells, monocyte-derived nurse-like cells, and T cells in those niches enhance CLL cell survival and confer chemoresistance [34]. Such interactions occur through engagement of the BCR, chemokine receptors and tumor necrosis factor family member receptors (e.g., CD40, "B-cell activation factor receptor" BAFF-R among others). Both BCR and CD40 signaling upregulates activity of transcription factor NF κ B and the anti-apoptotic proteins Bcl-2, Mcl-1, Bcl-X and others, thus perpetuating CLL cell survival [35, 36].

In our laboratory we have modeled the CLL lymph node niche by establishing a co-culture of primary patient-derived CLL cells with CD40L-expressing fibroblasts. Using this model, we demonstrated feasibility of pharmacologic targeting NF κ B in CD40-activated CLL cells [37, 38]. Others have shown that treatment with ibrutinib abrogates BCR signaling-mediated NF κ B pathway activation *in vitro* and *in vivo* [39].

Recognizing that BAFF/APRIL ("a proliferation inducing ligand") signaling is an important pro-survival mechanism in normal and neoplastic B cells and BAFF-R is highly expressed in CLL [30], we established a unique co-culture model with BAFF-expressing CHO cells. In this model CLL cells a) are resistant to spontaneous apoptosis and chemotherapy (fludarabine, bendamustine); b) upregulate NF κ B (Appendix F, Fig. 1); and c) induce the anti-apoptotic proteins Mcl-1 and Bcl-X. Using this new model, we have shown that entospletinib induces apoptosis of BAFF-stimulated CLL cells, more potently than ibrutinib (Appendix F, Fig. 2). Like ibrutinib, entospletinib abrogated canonical NF κ B activation in BAFF-stimulated CLL cells (Appendix F, Fig. 3). Pharmacologic inhibition of Syk (R-406) also downregulated Mcl-1 in BAFF-stimulated cells (Appendix F, Fig. 4).

In this study, we will assess the effects of *in vivo* SYK inhibition on the activity of the canonical and non-canonical NF κ B as well as expression of the pro-survival Bcl-2 family members.

3.0 STUDY POPULATION

3.1 Inclusion Criteria

3.1.1 Patients who are \geq 18 years of age, who have the following diagnosis:

Phase I portion of the study:

- histologically or flow cytometry confirmed diagnosis of B-CLL/SLL according to NCI-WG 1996 guidelines [40].
- the following types of NHL as documented by medical records and with histology based on criteria established by the WHO:
 - Mantle cell lymphoma (MCL),
 - Follicular lymphoma (FL) - grades 1-3a,
 - Lymphoplasmacytic lymphoma (LPL),
 - Marginal zone lymphoma (MZL),
 - CLL in Richter's transformation,
 - B-cell prolymphocytic leukemia
- patients with histologically confirmed classical Hairy cell leukemia (HCL)

Phase II portion of the study

- histologically or flow cytometry confirmed diagnosis of B-CLL/SLL according to NCI-WG 1996 guidelines. Patients who lack CD23 expression on their leukemia cells should be examined for (and found NOT to have) either t(11;14) or cyclin D1 overexpression, to rule out mantle cell lymphoma.

3.1.2. Patients underwent \geq 1 prior chemotherapy-based or immunotherapy-based regimen or targeted therapy (e.g., inhibitors of BTK, PI3K etc.) administered for \geq 2 cycles, , and have had either documented disease progression or no response (stable disease) to the most recent treatment regimen.

Additional disease-specific criteria:

Patients with CLL/SLL must demonstrate active disease meeting at least 1 of the IWCLL 2008 criteria for requiring treatment [41]:

- i) A minimum of any one of the following constitutional symptoms:
 - Unintentional weight loss >10% within the previous 6 months prior to screening.
 - Extreme fatigue (unable to work or perform usual activities).
 - Fevers of greater than 100.5 F for ≥ 2 weeks without evidence of infection.
 - Night sweats without evidence of infection.
- ii) Evidence of progressive marrow failure as manifested by the development of, or worsening of anemia or thrombocytopenia.
- iii) Massive (i.e., >6 cm below the left costal margin), progressive or symptomatic splenomegaly.
- iv) Massive nodes or clusters (i.e., >10 cm in longest diameter) or progressive lymphadenopathy.
- v) Progressive lymphocytosis with an increase of $>50\%$ over a 2-month period, or an anticipated doubling time of less than 6 months.
- vi) Autoimmune anemia or thrombocytopenia that is poorly responsive to corticosteroids.

Patients with HCL must be intolerant of or not candidates for purine analog-based therapy, or failed to achieve response (CR or PR) or relapsed within 2 years of such therapy, AND meet the standard treatment initiation criteria (ANC $\leq 1000/\mu\text{L}$, Hgb $\leq 10 \text{ g/dL}$, platelet count $\leq 100,000/\mu\text{L}$).

Patients with indolent lymphoma (FL, LPL, MZL) and patients with B-cell prolymphocytic leukemia must have an indication for treatment in the opinion of the investigator.

Patients with MCL and patients with CLL in Richter's transformation should have previously received or not be candidates for high dose chemotherapy/autologous stem cell transplant.

3.1.4 For diseases other than CLL, LPL, and HCL, presence of radiographically measurable lymphadenopathy or extra-nodal lymphoid malignancy (defined as the presence of ≥ 1 lesion that measures ≥ 2.0 cm in the longest dimension [LD] and ≥ 1.0 cm in the longest perpendicular dimension [LPD] as assessed by CT or MRI). For LPL, measurable disease will be defined as serum monoclonal IgM $> 0.5 \text{ g/dL}$ or meeting at least 1 of the recommendations from the Second International Workshop on LPL for requiring treatment (Appendix E).

3.1.4 Patients must have ECOG performance status ≤ 2 (Refer to Appendix D).

3.1.5 Patients must have organ function as defined below:

- i) direct bilirubin $\leq 2 \times$ institutional ULN (unless due to known Gilbert's syndrome or compensated hemolysis directly attributable to CLL)
- ii) AST or ALT less than $2.5 \times$ institutional ULN
- iii) estimated CrCL using the Cockcroft-Gault equation $\geq 50 \text{ mL/min}$ (see Appendix B).
- iv) platelets $\geq 50,000/\text{mm}^3$ independent of transfusion support, with no active bleeding, and absolute neutrophil count (ANC) $\geq 1000/\text{mm}^3$, unless due to disease involvement in the bone marrow.

3.1.6 Ability to understand and the willingness to sign a written informed consent document.

3.2. Exclusion criteria

3.2.1 Prior therapeutic intervention with any of the following:

- therapeutic anticancer antibodies within 4 weeks (rituximab), except within 6 months for obinutuzumab or a similar investigational type II monoclonal

- antibody;
- radio- or toxin-immunoconjugates within 10 weeks;
- inhibitors of BTK (ibrutinib), PI-3K (idelalisib), BH3-mimetic venetoclax, lenalidomide and other “targeted” therapy (including but not limited to investigational BTK and PI-3K inhibitors, etc.) – within 6 half-lives (i.e., 36 hours for ibrutinib)
- all other chemotherapy, radiation therapy within 3 weeks prior to initiation of therapy.
- SYK inhibitors at any time

3.2.2 Inadequate recovery from adverse events related to prior therapy to grade ≤ 1 (excluding Grade 2 alopecia and neuropathy).

3.2.3 Chronic use of corticosteroids in excess of prednisone 30 mg/day or its equivalent.

3.2.4 Stem cell transplant recipients must have no evidence of and not receive treatment for graft-versus-host disease.

3.2.5 Concomitant use or use in the prior two weeks of moderate or strong CYP3A and CYP2C9 inducers or strong CYP2C9 inhibitors (Appendix C), including nutraceutical preparations, e.g., grapefruit juice and St John’s Wort.

3.2.6 History prior malignancy except:

- malignancy treated with curative intent and no known active disease present for ≥ 2 years prior to initiation of therapy on current study;
- adequately treated non-melanoma skin cancer or lentigo maligna (melanoma in situ) without evidence of disease;
- adequately treated in situ carcinomas (e.g., cervical, esophageal, etc.) without evidence of disease;
- asymptomatic prostate cancer managed with “watch and wait” strategy;
- myelodysplastic syndrome which is clinically well controlled and no evidence of the cytogenetic abnormalities characteristic of myelodysplasia on the bone marrow at screening.

3.2.7 Uncontrolled immune hemolysis or thrombocytopenia (positive direct antiglobulin test in absence of hemolysis or history of immune-mediated cytopenias are not exclusions).

3.2.8 History of Human Immunodeficiency Virus (HIV) infection or active hepatitis B or C.

3.2.9 Major surgery (requiring general anesthesia) within 2 weeks prior to initiation of therapy.

3.2.10 Inability to swallow and retain an oral medication. Patients with clinically significant medical condition of malabsorption, inflammatory bowel disease, chronic conditions which manifest with diarrhea, refractory nausea, vomiting or any other condition that will interfere significantly with drug absorption are excluded. Patients must also have adequate venous access

3.2.11 Need for ongoing therapy with proton pump inhibitors. H2 antagonists are allowed.

3.2.12 Active uncontrolled infection

3.2.13 Women who are pregnant or lactating

3.2.14 Fertile men or women of childbearing potential unless 1) permanently sterile or 2) using a highly effective measure of contraception such as condoms in males and consistent and correct use of one of the following in females: intrauterine device, tubal sterilization, Essure micro-insert system, vasectomy in the male partner. Effective contraception is required for males during treatment with study drug and to continue for 3 months after the last dose of either entospletinib or obinutuzumab, whichever is later. For women, effective contraception is required to continue for 18 months after the last dose of obinutuzumab or for 30 days after the last dose of entospletinib, whichever is later.

Definition of childbearing potential: for this study, a female subject is considered of childbearing potential until becoming post-menopausal unless permanently sterile or with medically documented ovarian failure. Women are considered to be in a post-menopausal state when ≥ 54 years of age with cessation of previously occurring menses for ≥ 12 months without an alternative cause. Women of any age with amenorrhea of ≥ 12 months may also be considered post-menopausal if their follicle stimulating hormone (FSH) level is in the post-menopausal range and they are not using hormonal contraception or hormonal replacement therapy. Permanent sterilization in females includes hysterectomy, bilateral oophorectomy, or bilateral salpingectomy in a female subject of any age. Permanent sterilization in males include bilateral orchectomy or medical documentation of alternative explanation.

3.2.15 Any condition for which participation in the study is judged by the Investigator to be detrimental to the patient with inter-current illness or psychiatric/social situations that would jeopardize compliance with study requirements.

4.0 REGISTRATION PROCEDURES

Accrual to this study will take place at the Knight Cancer Institute Center for Hematological Malignancies at Oregon Health and Science University (OHSU). Coordination of accrual for other participating sites will be centralized at OHSU.

4.1 Subject Registration

There is no randomization for treatment. This is a phase I/II dose escalation trial with an intention-to-treat all patients who are enrolled in this clinical trial. Potential subjects will be seen by investigators of this study as a new patient or consult visit or as a follow-up visit. Referral of potential subjects to co-investigators of this study is made as part of standard of care, with the referring physician seeking advice on the diagnosis, evaluation, and/or treatment of CLL and NHL.

4.1.1 Local registration.

Registration from all consented subjects must be entered into the electronic Clinical Research System (eCRIS). Registration of OHSU patients will include the minimum of the following:

- A completed Eligibility Checklist signed by the investigator
- Signed copies of the most recently IRB-approved, informed consent form and HIPAA authorization

5.0 TREATMENT PLAN

5.1 Administration of study agents.

This is an open-label, Phase I/II trial with a dose escalation phase. The primary objective of the dose escalation phase is to determine the recommended phase 2 dose (RP2D) of entospletinib in combination with obinutuzumab in patients with relapsed/refractory CLL and B-cell malignancies. The Phase II portion will further evaluate the efficacy and safety of this novel combination.

Treatment will be administered on an outpatient basis but will also be permitted inpatient.

Reported adverse events and potential risks associated with entospletinib and obinutuzumab are described in Section 7. Appropriate dose modifications for both drugs are described in Section 6. No investigational or commercial agents or therapies other than those described below may be administered with the intent to treat the participant's malignancy.

The timing of study assessments and procedures is presented by study cycle and day and are abbreviated by the following references: Cycle (C) and Day (D) number, as in C1D1 (Cycle 1 Day 1). Cycles and days within each week are numbered sequentially thereafter.

Entospletinib will be administered as single agent for 7 days (during the run-in phase (days -7 to -1) for the purpose of correlative studies, followed by a combination with obinutuzumab (beginning with C1D1). C1D1 will occur immediately after Day -1 of the run-on phase (i.e., there is no "day 0").

Table 1. Treatment description

Agent	Pre-medications; Precautions	Dose	Route	Schedule	Cycle Length
Entospletinib*	None	According to dose level- see below	PO	BID or daily on Days -7 to -1 (run-in phase), and then beginning with C1D1	
Obinutuzumab	Benadryl Tylenol Dexamethasone	3000 mg split dosing in cycle 1, 1000 mg with each subsequent cycle	IV	C1D1 – 100 mg C1D2 – 900 mg C1D8 & 15 – 1000 mg Day 1 of cycles 2-6 – 1000 mg	28 days (4 weeks)

* The morning dose of entospletinib will be administered in the clinic on day -7 of the run-in phase, and subsequent doses will be self-administered

5.1.1 Phase I (Dose Escalation)

Patients with CLL/SLL as well as all other histologic categories of NHL will be enrolled, as specified in the eligibility criteria.

Up to three dose levels will be evaluated in the Phase I portion of the study. The dose levels of entospletinib are 200 mg po twice daily (Dose Level 1), 400 mg po twice daily (Dose Level 2) and 200 mg po daily (Dose Level -1) beginning with day 1 of cycle 1 (Table 2). The starting dose of entospletinib will be 200 mg po bid on day -7 of the run-in phase, and the same dose will be administered on day 1 of cycle 1, which will occur immediately following day -1 of the run-on phase. The first dose of obinutuzumab will be administered IV on day 1. The dose of obinutuzumab will remain unchanged at each dose level, and the last dose will be administered with cycle 6. Each cycle will last for 28 days.

Each patient will be treated for at least 12 cycles, or until a qualifying event (Section 5.4 – Duration of therapy). Both drugs will be administered during cycles 1-6, and entospletinib alone will be administered during cycles 7-12.

The dose escalation phase will follow a standard 3+3 Phase I design. At a given dose level, 3 patients will be enrolled. If all 3 patients complete ***the run-in phase and the first cycle of therapy*** (28 days) without any dose-limiting toxicities (DLTs), the next cohort of 3 patients will be enrolled at Dose level 2. If 1/3 patients develops a DLT the cohort will be expanded to 6 patients. However, if either $\geq 2/3$ or $\geq 2/6$ patients in dose

level 2 have DLTs, Dose level 1 will be defined as the MTD of the combination. The MTD will be considered RP2D and enrollment onto the Phase II part of the study will begin.

Table 2. Dose levels planned for dose escalation phase of the study

Dose Level	Entospletinib (Cycles 1-12 and thereafter) PO starting on Day -7 of the run-in phase	Obinutuzumab (Cycles 1-6) IV
-1*	200 mg daily	C1D1 – 100 mg; C1D2 – 900 mg C1D18 & 15 – 1000 mg C2-6 – 1000 mg on day 1
1	200 mg BID	
2	400 mg BID	

*Dose Level -1 will be studied only if more than one patient develops a DLT in Dose Level 1

For all the Dose Levels, should more than one patient develop a DLT in the respective Dose Level; the dose of entospletinib will be reduced according to the plan shown in Table 3. Should more than one patient develop a DLT in the Dose Level "-1", the study will be stopped.

The decisions to escalate or de-escalate the dose of entospletinib will follow the schema in Table 3.

Table 3. Decision rules regarding dose modification for Entospletinib

Dose level (entospletinib)	Number of Participants with DLT at a Given Dose Level with C1	Decision Rule
200 mg po daily (dose level -1)	0/3	Enroll Phase II part at this dose
	1/3	Enroll 3 additional subjects
	1/6	Enroll Phase II part at this dose
	> 2/6	STOP the study
200 mg po BID (START dose level 1)	0/3	Escalate dose to 400 mg BID
	1/3	Enroll 3 additional subjects
	1/6	Escalate dose to 400 mg BID
	> 2/6	De-escalate dose to 200 mg daily
400 mg po BID (dose level 2)	0/3	Enroll Phase II part at this dose
	1/3	Enroll 3 additional subjects
	1/6	Enroll Phase II part at this dose
	> 2/6	Enroll Phase II at Dose level 1.

If no significant toxicities are observed, the dose escalation part of the study is anticipated to enroll between 6 and 12 patients. Any patient discontinuing study treatment prior to completion of the first cycle for reasons other than AEs related to the study drugs will be replaced.

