13.1 Study Design

Phase I Study Design

This is an open-label, phase I/II, dose-finding study in which safety and tolerability of escalating doses SYK inhibitor entospletinib (GS-9973) in combination with obinutuzumab in patients with relapsed/refractory chronic lymphocytic leukemia/small lymphocytic lymphoma (CLL/SLL) and NHL (FL, MCL, LPL, MZL). Since best responses for both entospletinib and obinutuzumab have been documented in CLL/SLL, the Phase II portion of the study will be limited to those patients, however additional expansion cohorts may be considered at a later date.

For the dose finding part of the study, Dose escalation will proceed within each cohort according to the following scheme. Dose-limiting toxicity (DLT) is defined in the section 5.2. The starting dose of entospletinib will be 200 mg po bid daily with one dose escalation (dose level 2) and 1 dose de-escalation. Entospletinib will be administered as a single agent for 7 days prior to C1D1 to allow for assessment of biomarkers.

Table 13. Dose levels planned for dose escalation phase of the study

Dose Level	Entospletinib (Cycles 1-12)	Obinutuzumab (Cycles 1-6) IV
-1*	200 mg daily	C1D1 – 100 mg; C1D2 – 900 mg
1	200 mg BID	C1D8 & 15 – 1000 mg
2	400 mg BID	C2-6 – 1000 mg on day 1

*Dose Level -1 will be studied only if more than one patient develops a DLT in Dose Level 1

Determination of MTD

The dosage will follow the 3+3 traditional escalation rules, starts with 3 cohorts at a planned dose level. If 0 out of 3 patients experiences DLT, dose will be escalated to the next higher level at which 3 cohort will be enrolled. If 1 out of 3 patients experiences DLT, 3 more patients will be enrolled at the same dose level. Escalation will continue if 1 of 6 patients experiences a DLT. If 2 or more patients in any dose level except for the starting dose level experience DLTs, dosing will stop, and previous dose level is determined to be MTD, unless only 3 patients have been treated at that level (the tentative MTD). If 2 or more patients in the starting dose level experience DLT, dose will be de-escalated to the -1 dose levels. A tentative MTD becomes final when a total of 6 patients are treated with less than 2 DLT, or a total of 3 patients are treated with less than 1 DLT.

Phase II Study Design

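### Table 3, the named 3+3 decision table, has no row for 2/3, 3/3 or exactly 2/6 DLTs, and its printed threshold differs from the two-or-more rule used in the text

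*Combined protocol and SAP*

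**What the plan says.** Section 5.1.1 names the instrument for dose decisions: "The decisions to escalate or de-escalate the dose of entospletinib will follow the schema in Table 3". For each of the three dose levels, Table 3 lists four outcomes: 0/3, 1/3, 1/6 and a final adverse row. The adverse rows read:

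- level -1: "> 2/6 STOP the study"
- level 1: "> 2/6 De-escalate dose to 200 mg daily"
- level 2: "> 2/6 Enroll Phase II at Dose level 1"

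The surrounding text uses another threshold:

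- Section 5.1.1, level 2: "if either $\geq 2/3$ or $\geq 2/6$ patients in dose" level 2 have DLTs, level 1 becomes the MTD.
- Section 5.1.1, all levels: "For all the Dose Levels, should more than one patient develop a DLT in the respective Dose Level", the dose is reduced according to Table 3.
- Section 5.1.1, level -1: "Should more than one patient develop a DLT in the Dose Level '-1', the study will be stopped".
- The footnotes to the study schema, Table 2 and Table 13 open level -1 once more than one patient has a DLT at level 1.
- Section 13.1, starting level: "If 2 or more patients in the starting dose level experience DLT, dose will be de-escalated to the -1 dose levels". For other levels it also acts at two or more, and it makes an MTD final at six patients only with fewer than two DLTs.
- The study schema and 13.1 return the study to Phase I if two or more of the first six patients at the MTD have a DLT.

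**The concern.** Two DLTs is the boundary outcome of a 3+3 design, reached as 2/3 or as 2/6. A reader who goes to Table 3, as 5.1.1 directs, finds no instruction for it at any level. The all-levels sentence does not close the gap by itself, because it sets the trigger at more than one DLT and then refers to Table 3 for what to do. The explicit wording that names both 2/3 and 2/6 covers level 2 only.

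The MTD or RP2D is the primary endpoint of Phase I, and Phase II patients are treated at that dose. At level -1 the same rows concern whether the study continues. The table named for these decisions should settle each case without the reader having to assemble the answer from other sections.

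**Working it through.** **Inputs.** Cohorts of 3, expanded to 6 after 1/3 (5.1.1). Table 3 rows and text thresholds as listed above. The documents do not give a true DLT rate p, so 10% to 50% is assumed.

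**The plan's own figure.** Section 5.1.1 anticipates 6 to 12 Phase I patients, and 13.5 expects at most 12. Table 3 leads from level 1 to one other level (2 or -1), with 3 or 6 patients at each: 3 + 3 = 6 to 6 + 6 = 12. The figure is reproduced. It does not depend on the adverse threshold, so it cannot show which one was meant.

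**Coverage.** A cohort can end in seven ways, because expansion follows only 1/3 and the most that six patients can then show is 4/6.

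| Final outcome | Table 3 row | Text rule (two or more) |
|---|---|---|
| 0/3 | yes | not triggered |
| 1/6 | yes | not triggered |
| 2/3 | none | triggered |
| 3/3 | none | triggered |
| 2/6 | none | triggered |
| 3/6 | yes, adverse | triggered |
| 4/6 | yes, adverse | triggered |

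Four of seven have a row. Of the five that trigger the text rule, two do.

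**Probabilities.** Let q = 1 - p and e = 3pq², the chance of 1/3.

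- 2/3 or 3/3: 3p²q + p³
- exactly 2/6: e × 3pq² = e²
- 3/6 or 4/6: e × (3p²q + p³)

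At p = 0.30: e = 3 × 0.30 × 0.49 = 0.441. Then 2/3 or 3/3 = 0.189 + 0.027 = 0.2160; 2/6 = 0.441² = 0.1945; no row = 0.2160 + 0.1945 = 0.4105; adverse row = 0.441 × 0.216 = 0.0953.

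| p | 2/3 or 3/3 | Exactly 2/6 | No row | Adverse row | Two or more DLTs | Share of these without a row |
|---|---|---|---|---|---|---|
| 0.10 | 0.0280 | 0.0590 | 0.0870 | 0.0068 | 0.0939 | 93% |
| 0.20 | 0.1040 | 0.1475 | 0.2515 | 0.0399 | 0.2914 | 86% |
| 0.30 | 0.2160 | 0.1945 | 0.4105 | 0.0953 | 0.5057 | 81% |
| 0.40 | 0.3520 | 0.1866 | 0.5386 | 0.1521 | 0.6907 | 78% |
| 0.50 | 0.5000 | 0.1406 | 0.6406 | 0.1875 | 0.8281 | 77% |

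Sums can differ in the last digit through rounding.

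**If the sign in the table was meant as at least 2/6.** The 2/6 column moves to the covered side, and the probability of an outcome without a row falls to the 2/3-or-3/3 column: 0.028 at p = 0.10, 0.216 at 0.30, 0.500 at 0.50.

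**The case against.** The strongest reply is that the text already settles these cases. Every rule stated in words acts at two or more DLTs. In the all-levels sentence of 5.1.1 the trigger stands in the text, and Table 3 only supplies the destination. At level -1, 5.1.1 stops the study without reference to the table. Most of this stands: a careful reader can work out an action for each outcome. What remains is that the named table does not contain those actions.

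A second reply is that the printed sign may be an at-least sign that lost its bar when the PDF was read. That cannot be excluded without the source PDF. Against it, the sign is the same in all three rows, while at-least signs survive in the text just above. Nor would it supply rows for 2/3 and 3/3. One could stretch the row to them by reading 2/6 as a proportion, but the column is headed as a number of participants, and the 5.1.1 text lists the two cohort sizes separately.

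A stronger reading is tempting. A reader might infer that 2/6, not being above 2/6, lets a level be kept, so that two sites could reach different RP2Ds from the same data. Under that reading the chance of accepting a level at p = 0.30 would rise from 0.343 + 0.441 × 0.343 = 0.49 to 0.49 + 0.19 = 0.69 (unrounded 0.494 + 0.194 = 0.689). At 10, 20 and 40% it would move from 0.91 to 0.97, 0.71 to 0.86 and 0.31 to 0.50. The documents do not support this. Table 3 escalates or accepts only on 0/3 and 1/6; 13.1 finalises an MTD at six patients only with fewer than two DLTs; and the return-to-Phase-I rule counts Phase I patients, so it would be met by the same six. Accrual for other sites is coordinated centrally (4.0), and nothing suggests that sites set dose levels themselves.

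**Conclusion.** The point holds as a defect of the decision table. As printed, Table 3 sets its adverse threshold at 3 of 6, departs from every rule stated in the text, and has no action for three of the seven final outcomes. It is silent on those outcomes and does not give an instruction opposite to the text.

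Over assumed DLT rates of 10% to 50%, 9% to 64% of cohorts end on an outcome without a row (41% at a rate of 30%). These are probabilities of reaching a gap in the table, not of a wrong dose decision. They rest on the assumed rates and on independent patients with a common rate within a level. The acceptance probabilities under the objection are hypothetical and apply only if 2/6 were misread as acceptable. If the source PDF shows an at-least sign, the 2/6 part falls away and the missing 2/3 and 3/3 rows remain.

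**What to change.** Check the sign in the source PDF. Then reconcile Table 3 with the text of 5.1.1, the dose-level footnotes (schema, Table 2, Table 13), 13.1 and the return-to-Phase-I rule. One threshold should be printed everywhere, and each reachable outcome (0/3, 1/3, 2/3, 3/3, 1/6, 2/6 and above) should have exactly one stated action at each dose level. Level -1 needs its own check: 5.1.1 stops the study there, while the general sentence in 13.1 for levels other than the starting one refers to a previous level as the MTD. Which rule applies is for the sponsor to decide.

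The cost is a few corrected cells and an added row per dose level. No patients or procedures are added, and anticipated Phase I enrolment stays at 6 to 12.
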